Engagement (PC-1), Dissemination, and Implementation: In developing this proposal, we actively engaged with *patients, partner healthcare systems leadership, providers, and staff, local patient advocacy groups, and national organizations involved in CRC screening* and we will continue this engagement throughout the project. A separate research protocol was developed to address our plan for studying the facilitators and barriers to implementing a system for providing decision aids to patients, and for sending provider notifications.

Patients: *Development of proposed study:* The patient advisory board of our previous study repeatedly asked about ways to calculate CRC risk levels for individuals and said that they would find such information helpful. Members of our patient advisory board were involved in development and pilot testing of the personalized-messages and decision aid.

- *Involvement in upcoming study:* Four of the patients who served on the patient advisory board in the last study will serve as **patient consultants** and will attend research team meetings and work independently in concert with the team. Patient consultants will review and edit recruitment letters, phone call scripts, decision aids, and outcome measures. They will also continuously review our information regarding providing decision aids through the EHR patient portal. Patient consultants will get input from family and friends at key points. (PC-1)
- *Dissemination:* Patient consultants will accompany other research team members to national meetings, and may serve as panel members or discussants. (PC-4)

Leadership of partner healthcare systems: *Development of proposed study:* IU Health and Eskenazi leadership and quality improvement teams have always worked closely with our research team on CRC screening projects due to our shared interest in increasing CRC screening uptake rate. More recently, we have developed the proposal to provide decision aids through the patient portal of the EHR systems (Epic at Eskenazi, Cerner at IU Health). Both institutions wish to use these portals more frequently in patient care. We have worked closely with the information technology teams at both institutions to develop this plan and pilot the system at Eskenazi. (PC-1)

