6.0 Enrollment/Randomization

Patients: We will recruit patients from primary care clinics from two healthcare systems in Central Indiana: the IU Health Physicians' primary care practices of the Indiana University Health system (currently 34) and the primary care practices of Eskenazi Health (currently 9). These clinics serve a wide range of socioeconomic groups, including rural, upper-income suburban, middle-income urban/suburban, and lower-income urban (including 7 Federally Qualified Health Centers). Nineteen of the IU Health practices are outside of Indianapolis, and 4 are > 40 miles from the academic health center. (PC-2)

Clinical Information Specialists at IU Health will identify potentially eligible patients who have an upcoming appointment using a query of their electronic health record (Cerner) and will share that list with the research team weekly or biweekly. Eskenazi Health's potentially eligible patients will be identified by the Regenstrief Data Core, also on a weekly or biweekly basis. Both health systems will save a list of potentially eligible patients, along with their medical record number (MRN), street address, phone number, upcoming clinic appointment date and healthcare provider, and EHR patient portal enrollment status in a secure server accessible by the project manager and data manager. These lists will be updated on a regular basis throughout the recruitment period.

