Providers: The providers will be identified through each health system's provider directory, and confirmed and updated by the practice administrators. All eligible providers will be sent a letter and study information sheet explaining the study (see Notes & Attachments for letter and SIS), and be given the opportunity to let the research team know if they choose not to participate. Providers who agree to participate will be randomized to the Control group (receives a generic message) or the intervention

group (receives patient's ACN risk). The providers will be randomized based on a randomization scheme generated by our Biostatistics team.

The research team will not be blinded to provider assignment as they will need to know which notification to send. Providers will know that their patient enrolled in the study; however, the provider will be blinded to the patient's group assignment.

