10.0 Statistical Considerations

Sample Size Justification: This trial is powered for the two primary hypotheses. For Aim 1, we expect exposure to either personalized message will increase uptake from 30%, which was the uptake at six months seen in our current PCORI project, to 40% and the combined effect to be additive (i.e. no interaction between the interventions). We believe a 10% increase in uptake is a minimally important difference to detect. An earlier study found that patients who viewed a personalized message about risk of colorectal cancer had a 9% higher uptake than did those who viewed a non-personalized message (CI-2).⁴¹ We believe our intervention will have greater impact, due to its encouraging low-risk individuals (50% of patients)⁷ to use a non-invasive test. An earlier study found that individuals due for screening who were offered a non-invasive test had a 31% higher rate of screening than those offered just colonoscopy (69% vs. 38%)(CI-2).⁵ To detect an effect of 10% increase (odds ratio of 1.55) with a power

of 80% (two-sided $\alpha=0.05$) a sample size of 732 subjects (183 per group) is needed for the Wald test for either patient or provider message main effect in a logistic model if patient outcomes were independent. To account for clustering due to randomization by provider, we inflate the sample size based on the design effect. We assume an intraclass correlation of .05 for provider, and average number of subjects per provider of 8. (RC-3) We will allow for an attrition rate of 10%. This results in a final sample size of 1100 (275 per group). For the informed choice outcome, we expect exposure to either personalized message would increase informed choice from 20%, the outcome in our current PCORI project, to 30% (odds ratio of 1.71) and the effect to again be additive. This leads to an initial sample size of 604 total (151 per group) before accounting for inflation and attrition, which is less than for uptake. Thus, the sample size needed for both outcomes is 1100 (275 per group, 130 providers). These recruitment goals are readily achievable based on the INFORM study. Aim 2 is considered exploratory because we don't have sufficient preliminary data to estimate all effect sizes; however, we will have sufficient power for some hypotheses. (IR-1)

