Analytic plan: Preliminary analyses will compare baseline demographic information across the four groups using means and standard deviations for continuous variables and frequency distributions for categorical variables. We will adjust for those characteristics in subsequent analyses if significant differences emerge at a conservative level for inclusion of a covariate ($p<.20$). Characteristics of participants who don't complete T1 and/or T2 will be compared with those who remain to determine what biases may exist. The above analyses will be conducted using ANOVA, chi-square tests, or exact or non-parametric equivalents. If there appear to be biases in dropout, we will conduct pattern mixture models analyses to see how the results could change based on the missing data assumption (IR-5, MD-2, MD-3, MD-4). Primary analysis of outcomes will employ an intent-to-treat analysis. For Aim 1, our primary hypotheses will be tested using logistic regression models with the outcomes of informed choice and uptake (both yes/no outcomes) and main effects for: 1) patient receipt of personalized message; and 2) provider receipt of personalized message. A random effect for provider will be included to account for the clustered randomization. We will test for an interaction effect, but do not expect one so have not powered the study for an interactive effect. The secondary hypotheses (planned subgroup analyses with low risk group) will be tested using the same model type (HT-2, HT-3). The secondary hypotheses are considered exploratory. For Aim 2, mediation effects (RQ-6) will be estimated in a logistic regression setting, fitting the appropriate mediation models using MPlus⁷⁶ and then testing indirect effects using the percentile bootstrap approach to estimate the indirect effect.⁷⁷ For primary analyses, we will fit models that estimate the effects of either or both of the interventions relative to control. Moderators (RQ-4, HT-1, HT-2, HT-3, HT-4) will be identified by significant interaction terms in the regression models from Aim 1.

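### The plan does not say whether provider randomisation is stratified by health system, and the Aim 1 model names no health-system term

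*Combined protocol and SAP*

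**What the plan says.** **Allocation.** Section 6.0 (Providers) gives one sentence on method: "The providers will be randomized based on a randomization scheme generated by our Biostatistics team". It mentions no strata, blocks or balancing factors, and does not exclude them. The patient allocation is described just as briefly.

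**Setting.** Section 6.0 (Patients) states: "We will recruit patients from primary care clinics from two healthcare systems in Central Indiana". IU Health has 34 practices and Eskenazi Health has 9. On patient mix: "These clinics serve a wide range of socioeconomic groups, including rural, upper-income suburban, middle-income urban/suburban, and lower-income urban". That describes the clinics together and is not a contrast between the systems. Section 1.0 gives the record systems as "Epic at Eskenazi, Cerner at IU Health".

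**Size.** Section 10.0: "Thus, the sample size needed for both outcomes is 1100 (275 per group, 130 providers").

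**Model.** Section 10.0 (Analytic plan) specifies logistic regression with a main effect for each message, and adds: "A random effect for provider will be included to account for the clustered randomization". Baseline demographic characteristics are compared across the four groups and enter later models if they differ at p<.20. Health system is not mentioned as a model term or as one of those characteristics.

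**The concern.** Hypothesis 1.2 compares providers with providers. Its error is driven partly by how much uptake varies between providers, with about 65 in each arm. If the two systems differ in uptake, that difference forms part of the between-provider variation. The provider random effect carries it into the standard error but does not remove it; only a system term in the model does.

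The p<.20 rule is not a dependable substitute. It is written for demographics, and even if system were counted, it would enter only when imbalanced. The precision would then be forgone when the arms happened to be balanced, and the final model would depend on the data. Health system is known for every patient before randomisation, so neither limitation is necessary.

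At stake is some precision for one of the two primary hypotheses, plus protection against a chance imbalance of systems between provider arms.

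**Working it through.** **1. The plan's own figure.** Inputs from Section 10.0: uptake 30%, odds ratio 1.55, two-sided alpha 0.05, power 80%, ICC 0.05, 8 patients per provider, attrition 10%.

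N = 2(z₀.₉₇₅ + z₀.₈₀)² [1/(p₀q₀) + 1/(p₁q₁)] / (ln OR)²

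With p₀ = 0.30 and OR 1.55, p₁ = 0.399. Then 2 × 7.849 × 8.932 / 0.1921 = 730, or 732 in four equal groups, as stated. Design effect 1 + 7 × 0.05 = 1.35; 732 × 1.35 = 988.2; 988.2 / 0.90 = 1098, against 1100 stated. With 990 analysable patients, power for the provider effect is 80.2%. The stated figure reproduces and leaves almost no margin above its target.

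**2. Assumptions the documents do not supply.** The smaller system's share of providers is taken as its share of practices, s = 9/43 = 0.209. The difference in uptake between systems, d, is taken as 5 to 20 points.

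**3. Chance imbalance without strata.** With 130 providers split 65:65, the SD of the between-arm difference in s is √(0.209 × 0.791 × 4/130) = 0.071, a 95% range of about ±14 points. For shares of 20% to 50%, an imbalance of 10 points or more has a probability of about 12% to 29%. The resulting shift in the unadjusted estimate is imbalance × d. For d = 10 points the SD is 0.7 points (95% range ±1.4); for d = 20 the 95% range is ±2.8. The target effect is 10 points.

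**4. Gain from adjusting, if ICC 0.05 includes system variation.** This is worked on the risk scale as an approximation to the logistic mixed model.

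- Mean uptake 0.35, so v = 0.35 × 0.65 = 0.2275. Between-provider variance = 0.05 × 0.2275 = 0.0114.
- Patients per provider = 990/130 = 7.6. Variance of a provider mean, V = 0.0114 + 0.95 × 0.2275/7.6 = 0.0398.
- System component, B = s(1 − s)d² = 0.1655 d².
- Power after adjustment = Φ(2.802 × √(V/(V − B)) − 1.960), starting from 80%.

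| d (points) | B | B as share of between-provider variance | Power |
|---|---|---|---|
| 5 | 0.0004 | 4% | 80.4% |
| 10 | 0.0017 | 15% | 81.6% |
| 15 | 0.0037 | 33% | 83.7% |
| 20 | 0.0066 | 58% | 86.6% |

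For shares from 20% to 50%, starting from 80.2% with 8 patients per provider, a 10-point difference gives 81.8% to 82.7%.

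**5. The other reading of the ICC.** If 0.05 is the within-system value and system is ignored, the variance is multiplied by 1 + B/V, with V = 0.0384 at 8 patients per provider. Power falls from 80.2% to 79.5–79.8% for 5 points, 77.7–78.6% for 10 and 70.6–73.9% for 20, over shares of 20% to 50%.

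**6. Strata or model term?** A provider-level simulation (8,000 runs per setting) used a 20-point difference and 35% of providers in the smaller system:

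| | System not in model | System in model |
|---|---|---|
| Unstratified | 71% | 79% |
| Stratified | 73% | 79% |

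Adjusted power sits near the 80% base, so this corresponds to the within-system reading of the ICC. Analytically, with system in the model, leaving out strata raises the variance by about 129/128, or 0.8%, and power moves from 80.2% to 79.9%.

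**The case against.** The strongest reply is that silence is not a decision. A scheme prepared by biostatisticians may well be stratified, and a reader who infers that providers are randomised without strata goes beyond Section 6.0. That stands: the gap is in what is specified.

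A reader might also infer that the two systems are very different. The documents do not show it. The socioeconomic range is given for all clinics together, the Federally Qualified Health Centers are not assigned to a system, and no uptake by system appears. One study team sends the provider message in both systems (Section 7.1), and one data core queries uptake for both (Section 7.2). Different EHR vendors make a difference in uptake or its capture possible but do not establish one.

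A third tempting reading is that the trial is underpowered because strata are missing. Neither half is supported. If ICC 0.05 already contains the system difference, 1100 patients pay for it and the 80% target holds; adjustment is then an optional gain. The losses in step 5 need the opposite reading, which the plan does not state. And nearly all the recoverable power comes from the model term, not from strata.

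Finally, randomisation keeps the provider estimate unbiased, and the shifts in step 3 are small against a 10-point effect. That also stands. The p<.20 rule is only a partial answer, since it does not name system and acts only on observed imbalance.

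**Conclusion.** The point holds as a gap in specification with an inexpensive improvement attached. The provider scheme is not described, and system enters the Aim 1 model, if at all, only through a data-driven rule written for demographics. Prespecified adjustment is worth about 2 power points for Hypothesis 1.2 at a 10-point system difference, about 4 at 15, about 7 at 20, and under 1 at 5.

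These sizes rest on an assumed 21% provider share, assumed uptake differences, and the ICC of 0.05 including system variation. The documents fix none of the three. The result does not show that the sample size is wrong, that the systems differ in uptake, or that providers were randomised without strata.

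**What to change.** 1. Prespecify health system as a fixed effect in the Aim 1 and secondary models, whatever the observed imbalance, and record this before unblinding. Exempt it from the p<.20 rule.
2. State in Section 6.0 whether provider randomisation is stratified by health system. If it already is, one sentence suffices.
3. If providers are not yet randomised, stratify by system with permuted blocks within system. If they are, keep item 1 alone.

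The cost is one model term and, where still possible, two allocation lists in place of one. No patients, staff or procedures are added. If the systems turn out not to differ in uptake, the term costs about 0.3 power points at most.

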7.0 Study Procedures

Since the goal of the proposed research is to improve patient decisions regarding screening and prevention by testing an innovative approach to informing patients and their healthcare providers about personal risk for colorectal cancer, we require the involvement of both patients and healthcare providers.

7.1 Interventions

Patients:

Decision aid without personalized message (RQ-5): For the study, we have modified the “verbal” decision aid designed and tested in our study supported by PCORI (CDR-1403-11040). In this study, 688 patients eligible for screening viewed a decision aid that provided extensive information about CRC screening, including baseline risk of lifetime CRC mortality and incidence (no screening), risk reduction provided by colonoscopy and FIT, sensitivity of colonoscopy or FIT, and rate of FIT turning positive (requiring colonoscopy) and of complications from colonoscopy.⁵¹ Half the patients viewed a decision aid presenting this information using numbers and icon charts (quantitative arm); the other half viewed a decision aid presenting the information using only verbal descriptions (no numbers) (verbal arm).⁵¹

Viewing either decision aid in this project led to significant increases in mean intent to undergo screening (3.94 vs. 3.52, $p < .001$) and to undergo FIT (3.41 vs. 3.05, $p < .001$), both on a five-point scale, and lower decision conflict (18.8 vs. 39.5, $p < .001$). Compared to participants in the Verbal arm, those in the Quantitative arm had a larger increase in intent to undergo FIT ($p = 0.011$), and were more likely to switch their preferred test from non-FIT to FIT (28% vs. 19%, $p = .010$).⁵¹ There was no difference in uptake of screening at six months (about 30% in both arms) or test choice (RQ-5).

The current study's *decision aid without personalized message* consists of a PowerPoint presentation converted to mp4 (video) with text, photos, and an audio track, that is advanced by the viewer and can be viewed online. It begins with a 60 sec video on CRC screening produced by the Centers for Disease Control and Prevention (CDC), followed by slides summarizing the advantages and disadvantages of colonoscopy and stool testing with the fecal immunochemical test (FIT)⁵¹ and DNA+FIT (Cologuard). (See **appendix** for DA script)

Decision aid with personalized risk message (RQ-5): For the current study, we have modified two decision aids developed and tested in previous studies. Initially, we developed a decision aid that provides a personalized risk message based on the ACN risk rule to be used in this trial⁷ and pilot tested it with 96 patients (RQ5). Viewing this decision aid resulted in a significant increase in mean intent to get screened (3.22 vs. 2.68, $p < .001$), intent to have FIT (2.59 vs. 1.98, $p < .001$), intent to have colonoscopy (2.82 vs. 2.64, $p = .002$), and lower decision conflict (35.9 vs. 61.9, $p < .001$), compared to before viewing the decision aid. Of note, the groups with low and very low risk for ACN were combined into one group (“low risk”). Individuals with low ACN risk ($n=16$) were randomized to view a description of the advantages of FIT for people with low risk. Patients in this group who viewed this description had a larger increase in intent to undergo FIT than did those who did not view the information (-0.06 vs. +1.00, $p = .001$).

Patients in this pilot study received messages whether their risk of current ACN was low, intermediate, or high-average based on the ACN prediction rule, but did not receive more specific information about their ACN risk (i.e. 4%, 10%, or 22%).

Based on our previous studies showing mildly beneficial effects of providing quantitative information,^{51,52} we modified the decision aid to include an icon chart depicting this probability as a frequency, and we pilot tested that decision aid with 9 patients. While this small pilot test did not allow formal statistical testing, intent to be screened was increased or unchanged after viewing the decision aid, compared to beforehand, for all patients.

The current study's *decision aid with personalized message* will first present the *decision aid without personalized message* followed by additional PowerPoint slides converted to mp4 (video) with text, photos, and an audio track briefly explaining the risk tool, the participant's score on the 5 risk factors, total score, ACN risk, and implications for screening and test choice. (see Appendix for DA script)

The decision aid without personalized message is approximately 10 minutes and the additional slides with the personalized message take approximately another 4 ½ minutes to view.

Providers:

Provider personalized ACN risk message (RQ-5): We designed and pilot tested a personalized message for providers that discloses:

- the patient's ACN risk: low (combining low and very low categories), intermediate, or high-average,
- the predicted frequency of ACN on an icon chart: 4 per 100; 10 per 100; or 22 per 100, and
- implications for screening decision and test choice.

The personalized message was slightly modified from one tested by Skinner et al. (2015, 2016), which was found to increase discussion of CRC screening and uptake in some groups.^{41,42} Both messages list patient risk factors for CRC and guideline-consistent recommendations for screening. Our message differs from Skinner's in that it classifies the probability of having a current ACN as low-average, intermediate, or high-average, displays the probability on an icon chart, and recommends FIT for patients at low risk and colonoscopy for those at high-average risk. Like Skinner's, our message specifies that both tests are acceptable for average-risk patients.

We tested the modified provider message with six primary care providers (5 MDs and 1 NP), each of whom viewed messages for four or five patients from their clinic who participated in the pilot testing of the final decision aid (28 evaluations total). Providers estimated the patient's risk of current ACN (low, average, or high) before and after viewing the message, and they changed their estimate in 17 of 28 evaluations (61%). The providers' recommended screening test (colonoscopy, FIT, or either) changed after viewing the message in 16 of 28 evaluations (57%). For 26 of 28 evaluations, providers rated the information about ACN risk very helpful or somewhat helpful (PC-1).

For the current study, we have further modified the provider message based on feedback from IU Health and Eskenazi providers. The notification will include the patient's ACN risk (very low, low, moderate, high-average) and implications for screening decisions and test choice. Links to a web landing page containing a more detailed explanation of the risk tool and additional references will be included. (see Appendix for notifications and web landing page)

Providers randomized to the control group will receive a message informing them that their enrolled patient is due for CRC screening.

Providers will receive the message by email linked to the EHR system. The message will be sent by the research team within 24 hours of the provider's appointment with the enrolled patient.

